8.1.3 Secondary Efficacy Endpoints

Only the primary endpoint of %EWL and the secondary primary endpoint of 50% of the treatment group meeting the 25% EWL success criteria will be used to make product labeling claims. The data used to support the secondary endpoints will only be listed in data tables, and will not be considered statistically significant proof of efficacy.

8.1.4 Sensitivity Analyses

The efficacy analysis will be conducted on various populations for the purpose of conducting a sensitivity analysis. The first population is the per protocol population, that is, the analysis will be conducted on all treated subjects who complete the scheduled follow-up visits. A second analysis will be conducted on an intention to treat (ITT) population where the missing values at the 12 month time period will be imputed from the return to baseline methodology (i.e. all missing values at 12 months will be given the value at baseline). A third analysis used to perform efficacy analysis will use the Last Observation Carried Forward (LOCF) to impute the missing values. A fourth analysis will also be conducted: Missing values at the 12 month time period will be imputed using the mean value at 12-months of completers from %EWL quintile group such drop-out fell into at the time of drop-out. For example, if a subject were to drop-out at the 28th week and that subject fell

into the third quintile of %EWL at the 28th week, we would impute a %EWL at 52-weeks from that drop-out subject from the mean %EWL of the completers who were in the third quintile of %EWL at the 28th week. Analyses using the best and worst case scenarios will also be conducted. Finally, an analysis using multiple imputations will be conducted. In all the analyses where data is being imputed, any subject with a device related failure, or other obvious reasons that will lead to negative outcomes, will be evaluated as worst case for the AT group.

An additional sensitivity analysis for the secondary endpoints that are binary in nature will have the subjects who are lost to follow-up in the control group counted as successes and the subjects who are lost to follow-up in the AT group counted as failures.

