8.1.1 Efficacy Endpoints

The first effectiveness primary endpoint is the mean percent excess weight loss (%EWL) at 52-weeks. The hypothesis for the first primary effectiveness endpoint is that the difference in the mean percent excess weight loss (%EWL) at 52-weeks for the Aspiration Therapy (AT) group and Control group is at least 10%. %EWL is defined as absolute weight loss divided by baseline excess weight and multiplied by 100. Excess weight will be determined from ideal body weights based on a BMI=25 kg/m².

The second effectiveness primary endpoint is that at least 50% of the AT group at 52-weeks realizes a %EWL \geq 25%.

Sections 8.51 and 8.52 provide analysis of the sample size to meet co-primary endpoint #1 and #2, respectively with a power of 90% for each endpoint.

Since these endpoints are co-primary, the sample size is determined by the largest sample sizes required of the two primary endpoints. Co-primary endpoint #1 requires a sample size of 87 subjects (59 AT/ 29) to have a superiority margin of 10% EWL with a power of 90%, assuming an observed difference of 25% EWL and a standard deviation of both groups of 20%. Co-primary endpoint #2 requires a sample size of 99 AT subjects to realize that at least 50% of the AT groups realize >25% EWL at 52 weeks with a power of 90%, assuming an observed rate of 66% and a standard deviation of 20% of the AT group.

Co-primary endpoint #2 requires the largest sample sizes of the two primary endpoints, hence, not accounting for subject drop-out, a total of 150 subjects are needed in a 2:1 randomization (100 AT + 50 Control).

Since the primary analysis will be based on an ITT analysis using multiple imputations to estimate the missing values, the importance of over enrolling to have the exact number of evaluable patients has been lessened. However, to mitigate the effect of the imputation methodology on the control group, an over enrollment of ~15% for both groups is being proposed for a total enrollment size of 175 subjects (117 AT/58 Control).

8.1.2 Discussion on Drop-out Rate and Standard Deviation.

As 9% of the AT subjects (1 out of 11) in the Feasibility Study did not complete 52-weeks, we believe a 10% drop-out rate of the AT subjects for the Pivotal Study is a reasonable assumption. An over-enrollment of 15% (e.g., 117 AT subject versus 99 required) should readily accommodate the anticipated drop-out rate.

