A lower drop-out rate for the Controls (20%) is being assumed for the Pivotal Study than what was experienced in the Feasibility Study (43%; 3 out of 7 subjects). Although 20% is still higher drop-out rate than many drug studies, we believe that this drop-out rate for Controls should be anticipated given the disappointment some of the Controls will have in not being chosen as an AT subject. Data from a recently published article that compared bariatric surgery with intensive medical therapy in obese subjects with diabetes

support our estimate of a 20% drop-out rate. In that study, subjects were randomized into three equal arms: intensive medical therapy, gastric bypass, and sleeve gastrectomy^{62,} and the drop-out rate for the intensive medical therapy arm was 18% compared to 4% and 0% for the other two arms, respectively.

A standard deviation of approximately 25% in %EWL at 52-weeks was seen in both the AT and control groups. In the larger sample size associated with the Pivotal Trial, the extreme values will have a lessened impact on the variability of the observed responses. Hence, a reduction in standard deviation from 25%, as experienced in the Feasibility Trial, to an assumed 20% for the Pivotal Trial is realistic. The assumption of a 20% standard deviation is consistent with other obesity device weight loss studies. The Lap-Band PMA study had a 19% standard deviation at 1 year.⁶³ Similarly, the Realize Band study had nearly an 18% standard deviation at 1 year.⁶⁴

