8.5 Statistical Analysis Plan

All safety and efficacy analyses will be conducted on the intent-to-treat (ITT) population, defined as all subjects who undergo treatment in either the AT or Control group. Primary effectiveness analyses be performed without imputation; that is the "ITT evaluable" dataset will include only the observed data from each study visit. Imputation of missing values (e.g., using the methodologies outlined above) will be performed for subjects who terminate prematurely or are lost to follow-up. Those dropout subjects that have device-related adverse events, or other obvious reasons that lead to negative outcomes, will be imputed as failures in the primary analysis. As a sensitivity analysis the primary effectiveness endpoint will be re-analyzed using only data from completers.

A poolability analysis and covariate analysis will be performed. The demographic characteristics as well as the two primary endpoints will be examined for poolability across sites. The impact of important covariates will be examined for the two primary efficacy endpoints. These covariates will include race, age, gender, and initial BMI.

An internal, 6-month analysis will be performed on all endpoints to ensure systematic data collection at all sites and to identify potential safety concerns. The results of this analysis will not affect the clinical investigation plan unless a previously unidentified risk to study participants is discovered.

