8.5.2 Sample Size for Primary Endpoint #2 (Hypothesis Two)

Primary endpoint #2: At least 50% of the AT group at 52-weeks realizes a %EWL > 25%.

Hypothesis:

H₀: $\pi_{AT} \le 50\%$ H_a: $\pi_{AT} > 50\%$

Where π_{AT} is the proportion of patients who have a % EWL \geq 25% for the Aspiration Therapy group.

Using this hypothesis and the Fisher's exact test, the following table presents the sample size for the AT group with the assumptions listed in the table. The significance level is 0.025 and the power = 90%.

Table 8.5.2 Sample Size for Hypothesis Two

Power	Expected Proportion					
	55%	60%	65%	66%	67%	70%
90%	1047	259	113	99	87	62

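### The quintile-mean fill in the fourth sensitivity analysis of Protocol 8.1.4 makes the endpoint #1 standard error about 5% to 11% too small at the planned drop-out

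*Protocol*

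**What the plan says.** Protocol 8.1.4 opens its list of analyses with this purpose: "The efficacy analysis will be conducted on various populations for the purpose of conducting a sensitivity analysis". The list is completers, return to baseline, last observation carried forward, the quintile fill, best and worst case, and multiple imputation.

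Under the quintile fill, a missing week-52 %EWL is "imputed using the mean value at 12-months of completers from %EWL quintile group such drop-out fell into at the time of drop-out". The worked example is a week-28 drop-out in the third quintile, who receives the mean week-52 %EWL of the completers who were in the third quintile at week 28. No random draw, repetition or variance correction is mentioned. Nor does the text say whether quintiles are formed within arm.

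One override, limited to AT subjects, applies to every imputed analysis: "any subject with a device related failure, or other obvious reasons that will lead to negative outcomes, will be evaluated as worst case". The last item on the list reads "Finally, an analysis using multiple imputations will be conducted".

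Section 8.5.1 names a two-sample t-test for endpoint #1, at significance level 0.025. For endpoint #2, section 8.5.2 says that π_AT "is the proportion of patients who have a % EWL" of 25% or more, so responder status comes from each subject's own value. On drop-out, 8.1.2 takes 10% for AT, and for the other arm "A lower drop-out rate for the Controls (20%) is being assumed", against 43% in the feasibility study.

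**The concern.** Filling with a cell mean is a single deterministic imputation. Each filled value raises n by one and adds nothing to the variance within its cell, so an ordinary t-test sees too many subjects and too small an SD. An analysis meant to show whether the result survives drop-out would then report a confidence interval narrower than its data justify.

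For endpoint #2, the imputed mean is compared with 25%. Drop-outs who share a quintile and a drop-out week therefore all become responders or all non-responders, whatever the spread of outcomes among the completers they resemble.

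**Working it through.** **Plan's own figures.**
- Endpoint #1 (margin 10, difference 25, SD 20, 2:1): control n = (1.96 + 1.2816)² × 20² × 1.5 / 15² = 28.02, so 29. With 58 AT this gives 87, as in Table 8.5.1.
- Endpoint #2 (66% against 50%): ((1.96 × 0.5 + 1.2816 × √(0.66 × 0.34)) / 0.16)² = 98.4, so 99, as in Table 8.5.2.

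The design inputs are therefore understood.

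**Inputs for the check.**
- From 8.1.1 and 8.1.2: 117 AT and 58 control; SD 20; drop-out 10% (12 AT) and 20% (12 control), or 43% (25 control).
- Assumed, not in the Protocol: correlation ρ of 0.6 to 0.9 between %EWL at drop-out and at week 52; random drop-out; normal data; quintiles within arm.

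**Formula.** For a normal variable, quintile membership explains 0.897 of its variance (quintile means ±1.400, ±0.532 and 0 SD). The share of week-52 variance between quintiles is B = 0.897ρ², and within quintiles W = 1 − B. With completer fraction f in an arm of size n:
- variance seen by the t-test: 400 × (B + W·f)
- actual variance of the arm mean: 400 × (B + W/f) / n

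**Example, ρ = 0.6.** B = 0.323, W = 0.677, f = 105/117 = 0.897 (AT) and 46/58 = 0.793 (control).
- Reported: AT 0.931, control 0.860, pooled 0.907. SE = √(400 × 0.907 × (1/117 + 1/58)) = 3.06.
- Actual: AT 1.077, control 1.177. SE = √(400 × (1.077/117 + 1.177/58)) = 3.43.
- Ratio 0.891, a shortfall of 11%. The one-sided error at the margin is 1 − Φ(1.974 × 0.891) = 3.9%.

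**All settings, no worst-case override.** The last two columns are from simulation with 10,000 trials per setting.

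| ρ | Reported SE / actual SE (formula, 20% control drop-out) | Shortfall | One-sided error | Simulated shortfall, 20% | Simulated shortfall, 43% |
|---|---|---|---|---|---|
| 0.6 | 3.06 / 3.43 | 11% | 3.9% | 11% | 23% |
| 0.7 | 3.09 / 3.40 | 9% | 3.7% | 10% | 19% |
| 0.8 | 3.12 / 3.35 | 7% | 3.3% | 8% | 14% |
| 0.9 | 3.15 / 3.30 | 5% | 3.0% | 4% | 10% |

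Repeat runs differ by one to two percentage points. At 43% control drop-out, the simulated one-sided error is 3.6% to 6.4%.

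**With the override.** The Protocol gives neither the share of AT drop-outs affected nor a worst-case value. Assume 0% EWL. At a true difference of 10, the AT mean is 18.25 (control 8.25, from an AT planning mean of 25 + 20 × 0.412 = 33.25 and a difference of 25). Setting k drop-outs to zero lowers the AT mean by 18.25k/117.
- k = 3 of 12 lowers it by 0.47, and the error becomes 1 − Φ(1.974 × ratio + 0.47/actual SE) = 2.9% at ρ = 0.6 and 2.1% at ρ = 0.9.
- k = 6 lowers it by 0.94, and the error becomes 2.1% and 1.5%.

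In simulation with k = 3, the SE is still 4% to 11% too small.

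**Endpoint #2.** With AT mean 33.25, the second-quintile mean is 33.25 − 0.532 × 20ρ, or 26.9, 25.8, 24.7 and 23.7 at ρ = 0.6, 0.7, 0.8 and 0.9. The true responder rates there are 55%, 52%, 49% and 44%. If the observed cell mean sits at these values, the fill scores 100%, 100%, 0% and 0%. Under random drop-out, 12/5 = 2.4 AT drop-outs are expected in that quintile. The simulated AT rate after the fill is 66.7%, 66.5%, 66.4% and 66.2%, against a true 66.0%.

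**The case against.** The strongest reply is that this is one of several deliberately simple scenarios, that multiple imputation is listed beside it, and that 8.1.1 says "the primary analysis will be based on an ITT analysis using multiple imputations to estimate the missing values". That limits the consequence. It does not correct the interval that this analysis would report.

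Under the planning assumptions no decision turns on it. At a true difference of 25, the test on filled data rejects in over 99% of trials. With the correct SE, power is still about 99% (at ρ = 0.6, 15/3.43 − 1.974 = 2.39). The error matters only for results near the 10-point margin.

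Return to baseline and last observation carried forward are also single fills. That is true, but here the filled value is by construction the centre of its cell, so variance is removed systematically.

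A statistical analysis plan, not shown, could add a variance correction, and the point would then fall away. The Protocol itself fixes the fill as deterministic and names an ordinary t-test.

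A reader might also infer stronger claims, which the text does not support:
- *Every drop-out gets the completers' mean.* The worst-case rule removes some AT drop-outs.
- *The analysis is anti-conservative outright.* With that rule, the type I error can be at or below 2.5%. Only the understated SE persists.
- *All drop-outs of a quintile flip together.* The quintile is taken at each subject's own drop-out week, so different weeks can give means on either side of 25%. Most quintile-by-week cells will hold no drop-out or one.
- *The AT rate could move by 5 points.* That needs all 12 drop-outs in the second quintile (12 × 0.5/117 = 5.1 points). Under random drop-out this has probability 0.2¹², about 4 in a billion.

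**Conclusion.** The point holds for the standard error. As written, the quintile-mean fill analysed by the planned t-test understates the endpoint #1 SE by about 5% to 11% at the planned drop-out, and by about 10% to 23% at 43% control drop-out. The size rests on the assumed correlation, random drop-out and within-arm quintiles. The direction was the same in every setting tried. The one-sided error at the margin is about 3% to 4% without the worst-case override, and roughly 1.5% to 3% when a quarter to a half of AT drop-outs are set to 0% EWL.

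For endpoint #2, the all-or-none scoring within a quintile and week is a flaw of method, with an expected effect of about 1 point or less on the AT rate.

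A reader might infer that the primary result is affected, because 8.5 says "Imputation of missing values (e.g., using the methodologies outlined above) will be performed for subjects who terminate prematurely or are lost to follow-up". That sentence does not single out the quintile fill, and 8.1.1 names multiple imputation for the primary analysis. The unclear wording between 8.1.1 and 8.5 is a separate matter. This remains a minor correction to a supportive analysis.

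**What to change.** In 8.1.4, keep the quintile grouping and the worst-case override. Replace the mean by random draws from the week-52 values of completers in the same arm who were in the same quintile at the drop-out week. Repeat the draws (for example 50 times), analyse each completed data set, and combine by Rubin's rules. Derive responder status for endpoint #2 from each drawn value. Naming the arm also settles whether quintiles are within-arm or pooled, which the text leaves open.

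The cost is a change of wording and a few lines of SAS, with no new data. The downside is a slightly wider interval for this one analysis.

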8.2 Statistical Methods

Tabulation of summary statistics, graphical presentations, and statistical analyses will be performed using SAS® software. Where not otherwise specified, the last pre-treatment (i.e. for treatment group, this is prior to the initiation of therapy) observation will be used as baseline for calculating post-treatment changes from baseline. The primary presentations and analyses will be based on data pooled across study centers. Relevant summaries for individual centers, or combinations of centers, may be presented for primary data. All testing and confidence intervals will use a significance level of 5%.

8.3 Demographic and Baseline Characteristics

All demographic and baseline characteristics will be tabulated by treatment group and a test of homogeneity between the treatment groups will be conducted. For continuous variables (i.e. age, height, weight) a t-test will be used. For categorical variables (i.e. sex, race), a Fisher's exact test or chi-squared test will be used. Medical history findings, physical examinations and concomitant medications will be tabulated by treatment group.

8.4 Adverse Events

The number of subjects with at least one adverse event will be tabulated for each treatment group. Differences between the two treatment groups will be tested using Fisher's exact test. Then number of adverse events for each treatment group will also be tabulated.

The number of subjects and the number of adverse events will be tabulated by severity, anticipated, and causality.

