7.1.2 Risks Associated with Stomas/ Fistulas and A-Tube

Risks related having a fistula/ stoma include: 1) abdominal discomfort/pain, 2) peristomal skin irritation/ inflammation, erythema and granulation tissue formation, 3) peristomal leakage and/or bleeding, 4) infection, 5) buried bumper syndrome and gastric erosion, 6) difficulty sleeping on abdomen,

reduced range of motion at the torso, 7) persistent fistula after tube removal, and 8) scarring and/or skin depression after tube removal.

Abdominal Discomfort/Pain. It is normal for subjects to have abdominal discomfort after endoscopic A-tube (or PEG tube) insertion, which subsides over several weeks. Subjects will be instructed to take over-the-counter pain medications such as acetaminophen as needed for 1 week after A-Tube placement. In addition, at discharge from the endoscopy suite, subjects will be given a 1-week prescription for pain medications that can be used to control abdominal discomfort. Supplementary pain medication will also be provided at the physician's discretion. The experience from the Feasibility Study found that musculoskeletal or neuropathic complaints (e.g. burning, pulling) after tube placement was effectively treated with general oral pain medications and/or medications for neuropathic pain. It was thought by the Sponsor and the Study Team that discomfort after the first few weeks was primarily associated with the "old" A-Tube design (e.g., ePTFE tube with helical ridges of exterior or tube). With the new A-Tube design implemented in September 2011, subjects report significantly greater comfort.

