Peristomal Skin Irritation, erythema, discharge and granulation tissue. Based upon our studies to date, skin irritation, erythema, discharge and granulation tissue formation are common, minor, and manageable, and most subjects reported at least one such complication. After the new A-Tube design was implemented in September 2011, subjects reported a marked decrease in discharge and greater comfort. Skin irritation and erythema can be treated with topical zinc oxide, or other topical creams/products and by making sure the Skin-Port is ~1 cm away from the skin to reduce irritation. It is normal for granulation tissue to form at the ostomy site of the A-Tube. If the granulation tissue is excessive, it is easily removed by topical application with silver nitrate sticks. The area should be swabbed with alcohol before and after treatment. Care should be taken to ensure that silver nitrate does not come into direct contact with normal skin tissue, fistula track, or A-Tube. In addition, subjects are taught to inspect their stomas and report any evidence of irritation, erythema, discharge and granulation tissue. clinical team is also instructed to examine the stoma at every visit, and treat, as necessary.

Peristomal leakage. Leakage can be caused by the tube by (i) failure of the stomach stoma to heal around the tube, (ii) enlargement of the stomach stoma (sometimes caused by an infection within the tract or mechanical forces from

excessive tube manipulation), or (iii) buried bumper syndrome. The tube should be checked to make sure it can move freely in and out within the fistula tract to rule out the possibility of a buried bumper. If there is no evidence of a buried bumper, the patient should be instructed (i) not to aspirate and (ii) to avoid any manipulation of the tube to allow the stomach stoma to heal and form a tight seal. If skin irritation or excoriation occurs, skin care recommended for peristomal irritation can be started. If leakage persists after seven days, the A-Tube can be removed for several days and the tract allowed to partially close. A new A-Tube can then be placed through the same site.

Infection. The use of prophylactic antibiotics has markedly reduced the risk of bacterial infection after PEG tube insertions. If an infection occurs at the A-Tube site, it can usually be successfully treated as an outpatient: oral antibiotics for a bacterial infection or topical cream/oral antifungal agent for a fungal infection.

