7.3.4 Definitions for Criteria of Relatedness of Adverse Events to Device

Unrelated: The timing of the clinical event to the product administration makes a causal relationship not possible, or, other drugs, therapeutic interventions or underlying conditions provide a strong explanation for the observed event. Alternatively, common medical knowledge makes causal relationship implausible.

Unlikely Related: The timing of the clinical event to the product administration makes a causal relationship unlikely, or, other drugs, therapeutic interventions or underlying conditions provide a sufficient explanation for the observed event. Alternatively, common medical knowledge makes causal relationship unlikely.

Possibly Related: The timing of the clinical event to the product administration makes a causal relationship equally likely or not likely, and, other drugs, therapeutic interventions or underlying conditions provide only a low probability explanation for the observed event.

Probably Related: The timing of the clinical event to the product administration makes a causal relationship probable, and, other drugs, therapeutic interventions or underlying conditions do not provide a sufficient explanation for the observed event

Definitely Related: The timing of the clinical event to the product administration makes a causal relationship certain and common medical knowledge makes causal relationship highly probable.

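### The one between-arm safety test stated in Protocol 8.4, Fisher's exact test on any adverse event, is driven mainly by tube and placement events that Control subjects cannot have, so its p-value says little about other harm

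*Protocol*

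**What the plan says.** Protocol 8.4 (Adverse Events) sets the safety analysis: "The number of subjects with at least one adverse event will be tabulated for each treatment group". It then states "Differences between the two treatment groups will be tested using Fisher's exact test". Breakdowns are descriptive: "The number of subjects and the number of adverse events will be tabulated by severity, anticipated, and causality". Section 8.2 sets a 5% significance level for all testing without saying whether it is two-sided.

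No other between-arm safety test is stated. Eating behaviour is a safety outcome in 2.3 but has no test. Section 5.1 compares bone density with baseline and with historical controls. The group comparisons in 8.5.4 concern secondary efficacy endpoints.

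On what AT subjects can be expected to report, 7.1.2 says "It is normal for subjects to have abdominal discomfort after endoscopic A-tube (or PEG tube) insertion". Of skin irritation, erythema, discharge and granulation tissue in the earlier studies, it says "most subjects reported at least one such complication". Section 7.3.1a classes the risks in 7.1.2 as device-related adverse events and has anticipated non-serious events recorded on the case report form.

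Relatedness in 7.3.4 is scored to the device. An event is unrelated, for example, where "The timing of the clinical event to the product administration makes a causal relationship not possible". Section 7.3.1 defines a treatment-emergent event by its onset or worsening after device placement.

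**The concern.** Subjects in the Control arm have no endoscopy, tube or stoma, so a large class of recorded AEs can occur in only one arm. Those events are known in advance and the protocol itself treats most of them as minor. A yes/no variable for any AE is largely filled by them in the AT arm. A subject who already counts because of stoma irritation cannot count again for hypokalemia or a gallstone. The test then mostly confirms that a gastrostomy produces gastrostomy events.

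The randomised Control could inform a different question: whether aspiration adds serious events, metabolic or gastrointestinal events, or weight-loss effects (7.1.3 and 7.3.1a item 6). Safety is part of the objective in 2.0, and the data for several of these contrasts are collected in both arms. The causality tables do not supply the contrast, because attribution to a device has no equivalent meaning in subjects without one. The same event could be scored as related in one arm and unrelated in the other.

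**Working it through.** Section 8.4 gives no AE rate, power or sample size for this test, so there is no figure of the plan's to reproduce. The check asks how often the test rejects when the therapy causes no harm beyond tube and placement events, and how far that changes when it does.

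**Inputs from the protocol.** 117 AT and 58 Control subjects (8.1.1); Fisher's exact test (8.4); 5% level (8.2), taken as two-sided.

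**Assumed inputs**, since the protocol gives only words:
- *s*, the share of AT subjects with a stoma, tube or placement AE: 55% (lowest plausible reading of *most*), 80% and 90%.
- *b*, the share with a background AE, equal in both arms: 40%, 60% and 80%.
- *h*, the share of AT subjects with any other therapy-caused AE: 0% or 20%.
- The three sources are independent.

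**Formula.** Control any-AE rate = *b*. AT any-AE rate = 1 − (1−*s*)(1−*b*)(1−*h*). For example, at *s* = 90% and *b* = 40%, the AT rate is 1 − 0.10 × 0.60 = 94.0% with no other harm and 1 − 0.10 × 0.60 × 0.80 = 95.2% with *h* = 20%. Rejection probabilities come from exact enumeration of all outcomes.

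| *s* | *b* (= Control rate) | AT rate, *h* = 0 → 20% | Rejection, *h* = 0 | Rejection, *h* = 20% |
|---|---|---|---|---|
| 90% | 40% | 94.0% → 95.2% | about 100% | about 100% |
| 90% | 60% | 96.0% → 96.8% | about 100% | about 100% |
| 90% | 80% | 98.0% → 98.4% | 97.4% | 98.4% |
| 80% | 40% | 88.0% → 90.4% | about 100% | about 100% |
| 80% | 60% | 92.0% → 93.6% | 99.8% | about 100% |
| 80% | 80% | 96.0% → 96.8% | 88.7% | 93.1% |
| 55% | 40% | 73.0% → 78.4% | 98.8% | 99.9% |
| 55% | 60% | 82.0% → 85.6% | 85.4% | 95.2% |
| 55% | 80% | 91.0% → 92.8% | 47.7% | 63.1% |

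At *s* = 90%, a 20% added harm moves rejection by at most 1 point. At *s* = 55% the test responds somewhat (by 1 to 15 points), but with no other harm it already rejects far above 5% in every row.

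**What a separated variable does.** Running the same test on AEs other than stoma, tube and placement events gives AT rate 1 − (1−*b*)(1−*h*) against *b*. At *b* = 40%, rejection is 4.2% for *h* = 0, 9.9% for *h* = 10% and 28.3% for *h* = 20%. At *b* = 60% it is 4.2%, 7.4% and 17.2%. The level is held and the variable responds to the right thing, but power is low.

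**Specific events.** Fisher power at these sizes is 61% for 12% vs 2%, 77% for 20% vs 5%, and 14% for 10% vs 5%.

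**Interval width** (normal approximation). For 10% vs 5%, the 95% half-width is 1.96 × √(0.10×0.90/117 + 0.05×0.95/58) = 7.8 points around a 5-point difference. For 52% vs 40% (*b* = 40%, *h* = 20%), it is 1.96 × √(0.52×0.48/117 + 0.40×0.60/58) = 15.5 points around a 12-point difference.

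**Which contrasts the data allow.** Table 3 gives Control subjects AE recording at 14 visits, repeated electrolyte panels, hemoglobin and hematocrit at weeks 14 and 28, and a blood count at week 52. Its DEXA and serum iron entries are at screening only, so neither has a post-baseline Control value.

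**The case against.** The strongest reply is that harms are reported anyway. Sections 2.3 and 7.2 commit to the incidence of serious adverse events whether or not device-related. Section 8.4 tabulates by severity, and the severity grades in 7.3.3 do not depend on cause. A reader with those tables by arm can compute a risk difference. This stands. Someone might infer from the any-AE test that the trial yields no usable randomised safety information; the documents do not support that.

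Second, no decision rests on the p-value. Success in 2.1 needs only the two effectiveness endpoints, and no safety hypothesis or margin is stated. That limits the consequence. It does not make the stated test informative.

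Third, the rates are guesses. The protocol says *most* and *normal*, and 7.1.2 adds that a tube redesign reduced discharge and improved comfort, so earlier experience may overstate *s*. This also stands. It would go too far to say that the AT rate will be close to 100% or that the test must be significant whatever the therapy does: at *s* = 55% and *b* = 80% it rejects only 48% of the time. The point survives at that corner because what rejection there is still comes largely from expected events.

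Fourth, event-type tables and confidence intervals are commonly left to a statistical analysis plan, and the adverse event guidelines (Appendix K) are not shown. Their absence here is no fault. The finding concerns the test that 8.4 does fix.

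Finally, the protocol does not say how relatedness is scored in Control subjects, so differential attribution is a risk built into the definitions and has not been shown to occur.

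**Conclusion.** The point holds as a criticism of the stated test. The any-AE p-value in 8.4 mainly reflects stoma, tube and placement events that are possible in one arm only, and it should not be read as evidence for or against other harm from aspiration. Under the assumed rates, rejection with no other harm is 97-100% at *s* = 90% and 48-99% at *s* = 55%, for background rates of 40-80%. These figures rest on independence, on full enrolment of 117 and 58, and on AE rates that the protocol does not give.

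Other harms remain visible descriptively through SAE incidence and the planned tables. What is missing from the stated analysis is a like-for-like contrast with Control: the device-based definitions of relatedness and treatment emergence do not transfer to that arm, and the one tested variable does not separate other harms from tube events.

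**What to change.** In Protocol 8.4, keep the any-AE count by arm as a description and drop its p-value. Report between-arm risk differences with 95% confidence intervals, regardless of attributed cause, for:

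1. subjects with an SAE;
2. subjects with any AE other than stoma-site, A-Tube or placement events;
3. named events ascertained in both arms, for example hypokalemia, anemia by hemoglobin, gastrointestinal events, gallstones, alopecia and dehydration.

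Leave bone density and serum iron out of item 3, since Control has no post-baseline measurement of either.

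The cost is a rewording of 8.4 and one additional AE grouping, best defined before data are reviewed by arm. No new data are needed. The intervals will be wide, as the half-widths of 7.8 and 15.5 points show, so 8.4 should say that they are estimates and that an interval including zero does not rule out harm.
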